- This Protocol Amendment allows for an extended follow up period from the 18 to 36 months after randomization. All patients enrolled in IXT5 will be invited to participate, regardless of whether they are still active in the 18-month study. *See specifications on next page*.

188

- 189 Rationale for Change
- 190 Given the higher rate of myopia progression observed in overminus group vs. non-overminus group
- between randomization and 12 months, the goal is to determine whether the overminus group
- 192 continues to have higher myopia than the non-overminus group or whether the two treatment groups
- will have similar myopia progression over the long term.

PROTOCOL AMENDMENT II (11-22-19) PROTOCOL CHANGE #6 (CONTINUED) EXTENDED FOLLOW UP BETWEEN 18 TO 36 MONTHS

196 197 198

195

This protocol change allows for an extended follow up period 18 to 36 months after randomization.

199 200 201

202

Objective

To compare long-term refractive error between subjects originally treated with either overminus spectacles or non-overminus spectacles as part of the 18-month randomized trial.

203204205

Protocol Specified Follow-up Visits

Visits will occur at 24 months (±3 months) and 36 months (±3 months) from randomization.

206207208

209

210211

213

214

215

216

217

218219

220

221

223

224

225226

227

228229

230

231232

235

236

237

238239

Study Procedures/Data Collection

- The following testing procedures will be performed in the following order: using similar methods as the 18-month visit except where noted.
- 1. Treatments used since the last visit
- 212 2. Visual acuity
 - Measured using the investigator's usual testing procedure using an optotype method.
 - Testing must be performed in current refractive correction.
 - If prism is currently prescribed, visual acuity testing should be performed with prism.
 - If deliberate overminus* is currently prescribed, visual acuity testing should be performed *with* the overminus correction.
 - If visual acuity is 20/32 or worse (75 letters or less) in either eye, a manifest refraction must be performed. If the examiner believes that the patient's current correction is not optimal, trial frames with new correction should be used for all testing at the visit. This includes testing visual acuity again, with the patient wearing trial frames.
- 222 3. Control of the Exodeviation #1 masked
 - Testing must be performed in current refractive correction.

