The parent/guardian of each subject will be compensated \$50 for completion of each of the 24-month and 36-month visits, up to a total of \$100. If there are extenuating circumstances, and the subject is unable to complete the annual study visits without additional funds due to travel costs, additional funds may be provided.

The study will pay for visits specific to the research study, but will not pay for usual care visits that would occur whether or not the subject was in the study. The cost of usual care visits will be the responsibility of the subject or his/her insurance company.

The study will pay for a pair of spectacles (lenses and frames) at the first extension study visit (24 months or 36 months). Spectacle changes / new spectacles prescribed at other times will not be paid for by the study.

Treatment after 18-months is at investigator discretion and is not part of this protocol. Any costs associated with treatment will not be paid for by the study.

Risks

The procedures in this study are part of daily eye care practice in the United States and pose no known risks.

Subject Contact During Follow Up

Between annual visits, subjects may be called periodically by the Jaeb Center to promote retention.

Re-consenting of Subjects

An addendum to the original informed consent form (and addendum to the assent form, if required) for the extension study will be signed by parents who elect to continue their child's study participation. Re-consenting will occur at the next 12, 15, or 18-month randomized trial visit but could occur at other times either before or after participation in the 18-month trial has ended. A subject (and respective parent) may withdraw from the study at any time.

294295 Statistical Analyses

The following analyses will be completed separately at the 24-month and 36-month visits to evaluate the effect of the overminus treatment approach followed by usual clinical care versus the non-overminus treatment approach followed by usual clinical care:

- Spherical equivalent refractive error will be compared between treatment groups using an ANCOVA model that adjusts for baseline spherical equivalent refractive error. The treatment group difference and a 95% confidence interval will be calculated.

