- Mean distance control (average of 3 measurements) will be compared between treatment groups using an analysis of covariance (ANCOVA) model, which adjusts for baseline distance control, distance PACT, age, refractive error, and use of ADHD medication, to address potential residual confounding.
- The proportion of subjects with no spontaneous tropia will be compared between treatment groups as in section 5.1.2.1.
- Axial length, flat corneal radius, anterior chamber depth, and lens thickness (if available) will be compared between treatment groups as in section 5.3.2.3 and
- Secondary outcomes of near control, angle magnitude, and near stereoacuity will also be compared between treatment groups as in section 5.3.1.
- Treatments used since the last visit will be tabulated by treatment group.

	PROTOCOL AMENDMENT I (11-8-16)
]	This amendment provides for the following protocol changes:
]	Protocol Change #1
r	Original Protocol At the time of enrollment and each follow-up visit at 6, 12, 15, and 18 months, parents are asked to respond to a survey of symptoms potentially associated with spectacle treatment (headaches, eye strain, and other problems with spectacle wear) based on their observations of their child in the past weeks.
(Changed Protocol
1	 To add a 7-question survey of intermittent exotropia symptoms to be administered to the child. To add a health-related quality of life questionnaire to evaluate whether either treatment impacts the effect of intermittent exotropia on quality of life.
	• Children ages 5 and older at the time of enrollment will complete an 11-item questionnaire to assess how their eye condition affects their quality of life. Children years of age and younger at the time of enrollment will not complete the child questionnaire.
	 A 16-item parental questionnaire will assess how the child's eye condition affects the quality of life of the parent (for all subjects).
3	3. The surveys and questionnaires will be completed at the time of enrollment; and at 6-month, 12-month, and 18-month follow-up visits.

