5.4.1 Refractive Error at 12 and 18 Months

- 1835 Mean 12-month spherical equivalent refractive error will be compared between treatment groups
- using an ANCOVA model which adjusts for baseline spherical equivalent refractive error. The 1836
- 1837 treatment group difference and a 95% confidence interval will be calculated.

1838

1839

Development of Esodeviation

- 1840 Development of any esodeviation will be tabulated by treatment group, indicating the magnitude
- 1841 of the esodeviation (by PACT) and whether it was a constant tropia, intermittent tropia, or a phoria.
- 1842

1843 1844

5.4.3 **Reduction of Distance Visual Acuity**

1845 Any cases of reduced visual acuity in best refractive correction (≥2 logMAR lines) in either eye 1846 will be tabulated by treatment group.

1847 1848

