459 spherical equivalent refractive error will be performed using an ANCOVA model which
460 adjusts for baseline refractive error and baseline age. The latter was added as a post-hoc
461 adjustment factor, as age is expected to be associated with refractive error at the 12-
462 month (and 18-month) time points. The treatment group difference, 95% confidence
463 interval, and p-value will be calculated. This analysis will be done combining refractive
464 error obtained by subjective refraction or retinoscopy and separately from refractive error
465 obtained by autorefraction.

466

467 **4.1.10 Quality of Life**

468 At both the 12-month and 18-month time points, a two-sided treatment group comparison
469 of the child, and each of the three parent scales in the IXTQ HRQOL (Quality of Life)
470 will be performed each using the Wilcoxon Rank Sum Test as it is expected that scores
471 will not be normally distributed and will have a substantial ceiling effect. The treatment
472 group difference, 95% confidence interval, and p value will be calculated for both the
473 Rasch-scored data¹ and for 0 to 100-scaled data. The reported p-value will be derived
474 from the analysis of Rasch-scaled data, while to aid in interpretation, the 0 to 100-scaled
475 data will be used when reporting the median values for each treatment group.

476

¹ Leske DA, Holmes JM, Melia M, on behalf of Pediatric Eye Disease Investigator Group. Evaluation of the Intermittent Exotropia Questionnaire using Rasch analysis. JAMA Ophthalmol 2015;133:461-5.

477 A potential secondary manuscript, to be detailed in a separate SAP, will describe quality
478 of life, IXT symptoms, and spectacle wear issues, the relationships among these, and
479 relationships between these and clinical measures.

480

481 **4.1.11 IXT Symptom Survey**

482 A 7-item survey of IXT-related symptoms will be completed by the child at the
483 enrollment, 6-month, 12-month, and 18-month outcome exams. For each IXT-specific
484 symptom, the child is asked how often it occurs, using the response choices of “never”

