724 **5.2.1. Principles to be Followed in Primary Analysis**

725 Model assumptions for the ANCOVA will be checked as described in Section 2.1.1,
726 including linearity of baseline refractive error, normal distribution, and equal variance
727 across treatment groups. If baseline refractive error was included as a continuous variable
728 in the analysis from Section 2.1, it will be included as a continuous variable in this model
729 as well; otherwise, it will be categorized.

730
731 There will be no imputation for missing data; however, baseline characteristics of
732 participants with and without follow up will be tabulated at each time point. In the event
733 there is a clinically relevant imbalance between those with and without follow up, a
734 propensity score-weighted analysis will be performed as a sensitivity analysis.

735
736 The primary analysis will follow a modified intention-to-treat principle, with all
737 participants analyzed according to their randomized treatment group. To be included in
738 the analysis, the 24-month visit must be completed no earlier than 630 days (≥ 21
739 months) and no later than 899 days (< 30 months) after randomization. If the 24-month
740 visit is not completed within this analysis window, the 18-month visit data will be used
741 instead (if available and if within 24-month window). The 36-month visit must be
742 completed no earlier than 900 days (≥ 30 months) and no later than 1440 days (≤ 48
743 months) after randomization.

744
745 As a sensitivity analysis, the primary analysis will be repeated but limited to participants
746 who completed each visit within the protocol window of +/- 3 months.

747 A separate sensitivity analysis will repeat the primary analysis but be limited to
748 participants who were not treatment crossovers at any point in the study.

749
750
751
752
753
754
755
756
757
758
759
760
761
762
763
764
765
766
767
768
769
770
771
772
773
774
775
776
777
778
779
780
781
782
783
784
785
786
787
788
789
790
791
792
793
794
795

5.3.Secondary Analysis—Comparison of Axial Length and Other Biometric Measurements Between Treatment Groups at 24 and 36 Months

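### The Protocol's 24- and 36-month refractive-error ANCOVA leaves out baseline age, which the SAP adds for the same outcome at 12 and 18 months

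*Protocol*

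**What the plan says.** The extension's stated objective is refractive error: "To compare long-term refractive error between subjects originally treated with either overminus" spectacles or non-overminus spectacles (Protocol Amendment II, Change #6, Objective). Its analysis list gives the model, to be fitted separately at 24 and 36 months: "Spherical equivalent refractive error will be compared between treatment groups using an ANCOVA model that adjusts for baseline spherical equivalent refractive error". No other covariate is named. The next item in that list, for distance control, uses a longer set: "which adjusts for baseline distance control, distance PACT, age, refractive error, and use of ADHD medication".

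The Protocol's own 12-month refractive-error analysis (section 5.4.1) has the same single covariate: "using an ANCOVA model which adjusts for baseline spherical equivalent refractive error".

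The SAP moved away from that at 12 and 18 months. Section 4.1.9 describes an ANCOVA that "adjusts for baseline refractive error and baseline age. The latter was added as a post-hoc" factor, and gives the reason: "adjustment factor, as age is expected to be associated with refractive error at the 12" and 18-month time points.

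For the extension, SAP 5.2.1 says the ANCOVA assumptions will be checked as in section 2.1.1, "including linearity of baseline refractive error, normal distribution, and equal variance" across the groups. It then gives a rule for entering baseline refractive error as continuous or categorized, and mentions no other covariate. Section 2.1.1, by comparison, lists all four covariates of the primary model, age among them, in its linearity check. The SAP 5.2 sentence that would define the extension model was not available for this review.

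**The concern.** The SAP treats baseline age as prognostic for refractive error at 12 and 18 months. Nothing visible explains why that reasoning should stop at 24 and 36 months, in children aged 3 to under 11 at entry. The extension was added to answer the refractive-error question, yet on the Protocol's wording age is adjusted for in the extension's distance-control model and not in its refractive-error model.

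Two things are at stake, both modest. The first is precision: a prognostic baseline variable left out of a linear model stays in the residual variance and widens the interval. The second is balance: randomization was stratified by site and baseline distance control (Protocol 2.6), not by age, so a chance difference in age between the arms among the children analysed would go unadjusted in the main model.

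**Working it through.** The documents give no sample size, power or standard deviation for the 24- and 36-month refractive-error comparison, so there is no stated figure to reproduce. The check has three parts.

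**1. The covariates side by side**

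| Source | Visits (months) | Covariates for refractive error |
|---|---|---|
| Protocol 5.4.1 | 12 | baseline refraction |
| Protocol Amendment II, extension | 24, 36 | baseline refraction |
| SAP 4.1.9 | 12, 18 | baseline refraction and baseline age |
| SAP 5.2.1 (assumption check only) | 24, 36 | only baseline refraction is named |

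The Protocol agrees with itself. The gap is between SAP 4.1.9 and the extension model as far as it can be read.

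**2. Precision**

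Input: R², the share of variance left after baseline refraction that age explains. The documents do not give it, so 1% to 15% is assumed.

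- With age included, the residual variance is multiplied by (1 − R²).
- Without age, the interval is wider by 1/√(1 − R²) − 1.
- Equivalent loss of children: a model with age needs N(1 − R²) children to match N children without it, so leaving age out costs a fraction R² of those followed.

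| R² (assumed) | 1/√(1 − R²) | Interval wider by | Equivalent loss if 300 are analysed (assumed) |
|---|---|---|---|
| 1% | 1/√0.99 = 1.005 | 0.5% | 3 |
| 5% | 1/√0.95 = 1.026 | 2.6% | 15 |
| 10% | 1/√0.90 = 1.054 | 5.4% | 30 |
| 15% | 1/√0.85 = 1.085 | 8.5% | 45 |

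**3. Chance age imbalance**

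With 1:1 allocation and N children analysed, the standardized age difference between arms has standard error √(4/N).

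- N = 384 (the planned total): √(4/384) = 0.102, so the 95% bound is 1.96 × 0.102 = 0.20 SD.
- N = 250 (assumed): √(4/250) = 0.126, so the 95% bound is 0.25 SD.

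An imbalance at that bound shifts the estimate without age by r × bound residual SDs, where r = √R².

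- r = 0.1 (R² = 1%): 0.02 SD at N = 384, and 0.025 SD at N = 250.
- r = 0.3 (R² = 9%): 0.06 SD at N = 384, and 0.07 SD at N = 250.

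In units of the estimate's own standard error this is 1.96r, that is about 0.2 at r = 0.1 and 0.6 at r = 0.3. The shift is random in direction and already counted in the wider interval of step 2. It is the same cost seen for one particular allocation, and not an additional one.

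**The case against.** The strongest objection is that the deciding sentence was not available. The Protocol's wording does not settle what the SAP does: for this same outcome at 12 months the Protocol also named only baseline refraction, and the SAP still added age. SAP 5.2.1 describes assumption checks and does not specify the model. It refers back to 2.1.1, which already covers age, and its list is introduced as inclusive. This stands in part. The omission can be stated for the Protocol and only inferred for the SAP. The inference is reasonable, because 2.1.1 names every covariate of its model while 5.2.1 names one and gives an entry rule for that one alone.

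A second objection is that adjusting for the baseline value of the outcome is a valid standard ANCOVA, and that age was a labelled post-hoc addition at 12 and 18 months. Both are true. The case for age is therefore that it improves the analysis, and the single-covariate model is not an error.

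The plan also has some protection against selective return. In SAP 5.2.1, "There will be no imputation for missing data; however, baseline characteristics of" those with and without follow-up will be tabulated, and a propensity-score-weighted sensitivity analysis follows if there is a clinically relevant imbalance. That addresses who returns. It does not directly adjust for an age difference between the arms, and it is conditional.

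Three stronger readings are tempting, and the documents do not support them:

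- *The comparison is biased.* Under 1:1 randomization, leaving out a baseline covariate does not bias the difference in means.
- *The 12/18-month and 24/36-month results cannot be compared because the models differ.* In a linear model both target the same mean difference at their visit. Adding a baseline covariate changes precision and not the target.
- *Age must matter more at two to three years than at one.* This may be expected, but the documents say only that age should be associated with refraction at 12 and 18 months.

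**Conclusion.** The point holds as a small, free improvement. The Protocol's extension model for refractive error has baseline refraction as its only covariate, and SAP 5.2.1 is consistent with that. SAP 4.1.9 treats age as prognostic for the same outcome at the two preceding visits. Leaving age out costs an interval about 0.5% to 8.5% wider, if age explains an assumed 1% to 15% of residual variance, and leaves a chance age imbalance unadjusted. That range has no source in the documents, and the true loss could be near its lower end. No stated figure is contradicted and validity is not threatened. If SAP 5.2 already includes age, what remains is to bring 5.2.1 into line.

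**What to change.** First check SAP 5.2. If age is not in the model there, add baseline age to the 24- and 36-month refractive-error ANCOVA, matching SAP 4.1.9. In either case, add age to the linearity check in 5.2.1, with the same continuous-or-categorized rule that baseline refractive error has. State whether the change was made before the 24- and 36-month data were examined, as SAP 4.1.9 labels its own addition. If the single-covariate model is kept on purpose, give the reason and report the age-adjusted model as a sensitivity analysis.

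The cost is a sentence or two in the SAP and one residual degree of freedom. Age is already recorded for every child, and no stated alpha, sample size or power changes.

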1.1 Intermittent Exotropia

Intermittent exotropia (IXT) is the most common form of childhood-onset exotropia with an incidence of 32.1 per 100,000 in children under 19 years of age. The onset of IXT is thought to often occur in the first year of life. Among children 1 to 2.5 years of age, IXT has been estimated to occur in 245 children per 100,000. IXT is characterized by an exotropia that is not constant and is mainly present in the distance but may also be present at near.

Treatment for IXT may be either non-surgical or surgical.⁴ While surgery is often considered for treatment of IXT, many cases of IXT are treated using non-surgical interventions,^{5,6} such as overminus lenses or occlusion.⁷

1.2 Overminus Lens Therapy

Overminus lens therapy involves prescription of additional minus power in the spectacle lenses and the spectacles are worn full-time.

Overminus lens therapy for exodeviations was described as early as 1913 by Landolt.⁸ In a survey of US and Canadian pediatric ophthalmologists,⁹ 52% reported that they routinely used some form of non-surgical therapy in the management of childhood IXT, with 34% of the 52% using overminus lenses. When the same survey was administered to members of the International Strabismological Association, half of the respondents said they used overminus lenses to treat childhood IXT.¹⁰

1.3 Possible Mechanisms of Overminus Lens Therapy

The mechanism of overminus lens therapy for IXT is uncertain. It is thought to work by stimulating accommodative convergence, therefore reducing the angle of exodeviation and allowing fusion, or by clearing distance blur (caused by excess compensatory accommodative convergence) and thus allowing fusion. An alternative hypothesis is that fusional convergence often induces convergence accommodation that results in distance blur, but this induced blur is mitigated by minus lenses allowing the better control of the IXT without blur. Regardless of the mechanism, overminus lens therapy may reduce the angle of the exodeviation, or increase the control of the exodeviation (reducing the amount of time the exodeviation is manifest), or both.

1.4 Short-term and Long-term Rationale for Using Overminus Lens Therapy

There appear to be two main reasons for implementing overminus lens treatment in IXT:

- As a temporizing measure to reduce the angle of the exodeviation, or increase the control of the exodeviation, or both, for example in a child considered too young for surgery or vergence training exercises.
- As a long-term strategy, to treat the IXT by improving control of the exodeviation, with eventual weaning of the overminus at a time when the child is well compensated in his or her regular refractive correction.

1.5 Public Health Importance of Proposed Randomized Clinical Trial

Although overminus lens treatment for IXT is widely used in clinical care, there have been no RCTs evaluating its long-term effectiveness. Evaluating the effectiveness of overminus lens treatment for IXT has important public health implications because successful treatment may reduce the proportion of children needing to undergo surgery. Conversely, evidence of poor treatment effectiveness with overminus lens therapy would prevent children from undergoing unnecessary treatment with overminus lenses.

1.6 Previous Studies of Overminus Lens Therapy

Previous studies of overminus lens therapy have been mainly limited to small case series, most with poorly defined methods of prescribing overminus, variable amounts of overminus prescribed, and poorly defined definitions of success (Table 1).

Table 1. Previous studies of overminus lens treatment for IXT

Author, Subject Method of over-minus Results		Commont		
year	population	determination	Results	Comment
Kennedy 1954 ¹³	N=103 successfully treated subjects (failures excluded)	Multiple tests of accommodation performed (described in detail by author). "Final lens selected is arrived at in light of all the data yielded by the various tests outlined, and is usually the lowest powered concave lens which produces objective orthophoria." Power may subsequently be changed.	Report only included successful subjects	Success defined as presence of one of the following: "cosmetically straight," "some fusion," or "constant fusion." Treatment duration not reported
Caltrider 1983 ¹⁴	N=35 N=10/35 seen 1 year after discontinuing overminus	Prescribed between 2.00D and 4.00D overminus. No other details provided.	46% qualitative improvement in overminus; 7/10 maintained improvement out of overminus	Qualitative improvement defined as neither parents nor physician noticing manifest exodeviation when wearing overminus. Treatment duration from 2 to 156 months

Author,	Subject	Method of over-minus	Results	Comment
year Goodacre	population	determination	62% "cured"	Cure defined as
1985 ¹⁵	N=34 aged 1 to 6 years	All prescribed 3.00D overminus initially. Amount of minus increased at follow-up if necessary to further improve control (up to a max of 5.00D overminus). No other details provided.	62% cured	exophoria near, distance, and far distance when wearing overminus lenses. Treatment duration at least 12 months
Rutstein 1989 ¹⁶	N=40 aged 1 to 15 years	Amount of overminus prescribed ranged from 0.50D to 3.75D. No other details provided.	Outcomes not described in terms of overminus success	Main outcome measure was change in refractive error (after wearing overminus). No treatment outcomes reported
Donaldson 1991 ¹⁷	N=18 aged 2 to 17 years	"Children of normal retinoscopy were generally ordered 2.00D, 2.50D or 3.00D overminus depending on the ophthalmologist's assessment of expected tolerance."	72% success	Success defined as binocular single vision for all distances & symptoms relieved when wearing overminus lenses. Treatment duration at least 6 months.
Reynolds 1994 ¹¹	N=74 aged 14 months to 13 years	Prescribed 1.00D to 2.50D overminus: the initial amount was "varied according to baseline refractive error and age of subject." No other details provided.	62% success	Success defined as conversion to orthophoria, pure exophoria, or IXT <10pd. Treatment duration at least 3 to 6 months
Kushner 1999 ¹⁸	N=74 mean age 4 years	Prescribed overminus spectacles "if seem beneficial in controlling deviation". For myopic refractions: additional 1.00D to 2.00D overminus. For hyperopic refractions: additional minus until final SE between -1.00D and -2.00D. In addition 4 to 6 prism diopters base in also incorporated in some cases. If satisfactory control not seen at first follow-up exam, added patching for anti-suppression	19% "improved control" without overminus correction 46% still in overminus 5 years later	Outcomes regarding effectiveness of overminus not clearly reported (study primarily on whether overminus causes myopia). Treatment duration from 6 to 156 months.

Author, year	Subject population	Method of over-minus determination	Results	Comment
Watts 2005 ¹⁹	N=24 aged 2- 17 years	Prescribed "maximum tolerated minus": minimum 2.00D to maximum 4.00D depending on ability to read 20/20 and N5 with overminus in place. Hyperopic subjects - Rx reduced by minimum of 2.00D, max 4.00D.	71%	Success defined as improved control (reduction in Newcastle control score) when wearing overminus. Treatment duration 3 months.
Rowe 2009 ²⁰	N=21 aged 1-9 years, Newcastle control score of 3 or worse	Prescribed minimum minus to reduce angle and achieve control of the manifest deviation at near & dist. Started with 1.00D and increased by 0.50D increments until control was achieved. Actual overminus initially prescribed: median 2.00D; range 1.00D to 3.00D.	24% success (out of overminus)	Success defined as exophoria at near, distance, and far distance, with binocular control at all distances OUT of overminus spectacles at 5 years follow-up. Treatment duration from 6 to 62 months in overminus and from 6 to 39 months out of overminus.
PEDIG 2015	N=58 aged 3- <7 years (n=27 overminus, n=31 non- overminus, Office control score 2 or worse (mean of 3 measures)	RCT: Reduce sphere by 2.50D in overminus group, non-overminus spectacles or no spectacles in non-overminus group	Mean control 2.0 vs 2.8 points favoring overminus. 59% success vs 39% success	Improvement in mean control score from baseline to 8 weeks while on treatment. Success defined as improvement of mean control score 1 point or more at 8 weeks while on treatment.

624 625

626

627 628

629

630 631

632

633

